5. EXCLUDED, PRIOR, AND CONCOMITANT MEDICATIONS

The study physician should assess all concomitant medications at every visit, and at the screening visit in particular to ensure that the subject is not taking excluded medications.

5.1. Prior Medications

Prior medications include all treatment, including but not limited to herbal treatments, vitamins, surgical implants (such as VNS), and prescribed medications received within 30 days (or PK equivalent of 5 half-lives, whichever is longer) of the date prior to screening. Prior treatment information, if available, must be recorded on the appropriate eCRF page.

5.2. Concomitant Medications

Concomitant medications refer to all treatment taken between the date of the first dose of IP and the date of the last dose of IP. Concomitant treatment information must be recorded on the appropriate eCRF page. Concomitant as needed (PRN) topical and intranasal steroids for dermatologic reactions and allergic rhinitis are allowed and do not warrant exclusion from study. If the subject is currently taking an excluded medication at the time of the screening visit, then the subject must undergo a washout period equivalent to 5 half-lives of the drug before they may enter the prospective 12-week baseline period.

Concomitant medications, other than AEDs, may be reduced or discontinued at the discretion of the investigator if medically warranted.

5.2.1. Concomitant Antiepileptic (AED) Medications

Concomitant AED regimens must have been stable for at least 1 month prior to the screening visit and must remain stable from screening to the end of the DB phase. Ketogenic diets and modified Atkins diets should be unchanged for 3 months prior to the screening visit and must remain stable throughout baseline and the DB phase.

Subjects with surgically implanted VNS will be allowed to enter the study provided that all of the following conditions are met:

- The VNS has been in place for \geq 1 year prior to the screening visit.
- The settings must have remained constant for 3 months prior to the screening visit and remain constant throughout baseline and the DB phase.
- The battery is expected to last for the duration of baseline and the DB phase.

Concomitant AEDs may be reduced or discontinued at the discretion of the investigator if medically warranted.

5.3. Rescue Medications

The use of rescue medication is allowed on an occasional basis and as medically needed. The type, dose, date, and frequency will be recorded.

5.4. Excluded Medications

Excluded medications include oral steroid medications, other IPs, ketoconazole and other investigational drugs or devices. Use of St. John's Wort and concurrent use of strong inducers or inhibitors of CYP3A4/5/7 is not permitted. A list of CYP3A4/5/7 inhibitors and inducers is included in Section 12.1. Any strong inhibitor or inducer of CYP3A4/5/7 must be discontinued at least 28 days before Baseline/Randomization Visit; note that this does not apply to approved AED medications.

Products containing tetrahydrocannabinol (THC) or non-approved CBD are excluded in the DB phase of the study but allowed in the OL phase. THC or non-approved CBD should be washed out for at least 2 weeks before screening. Subjects with a positive result on THC or non-approved cannabidiol CBD test (via plasma drug screen) can be retested, via plasma, after 2 weeks.

Note that if a subject is taking marketed Epidiolex (may go by another name in countries outside the United States) then the parent/caregiver will have to provide evidence of an active prescription or confirmation from prescriber.

Use of any herbal product or nutritional supplement must be reviewed and approved by Marinus Medical Monitor.

6. INVESTIGATIONAL PRODUCT

Both GNX and PBO will be packaged in high-density polyethylene (HDPE) bottles with a child resistant closure.

GNX will be supplied at a concentration of 50 mg/mL (GNX equivalent) in 120 mL bottles, containing 110 mL GNX. A PBO suspension, which is identical in taste and appearance, will be supplied at an equal volume.

All IP will be labeled according to regional regulatory requirements. At minimum, labels will contain the study number; a blinded bottle number; contents including quantity; dose and form; route of administration; storage conditions; instructions for IP administration; caution that this compound is an investigative drug intended for clinical trial use only; warning to keep out of reach of children; and the identity of manufacturer and sponsor. For those regions that require it, a blinded lot number and an expiry date will also be listed.

All IP will be stored at the research pharmacy prior to dispensing, or in a locked cabinet accessible only to members of the investigative research team after the completion of each study visit. Study medication should be stored at room temperature 15°C to 25°C (59°F to 77°F).

6.1. Identity of Investigational Product

6.1.1. Ganaxolone

Manufacturer: Catalent Pharma Solutions, Somerset, NJ 08873 USA

Vehicle: The suspension contains GNX (50 mg/mL), hydroxypropyl methylcellulose, polyvinyl alcohol, sodium lauryl sulfate, simethicone, methylparaben, propylparaben, sodium benzoate, citric acid, and sodium citrate at pH 3.8 to 4.2, and is sweetened with sucralose and flavored with artificial cherry.

Strength: 50 mg/mL suspension; 110 mL in 120 mL high-density polyethylene bottles

6.1.2. Placebo

Manufacturer: Catalent Pharma Solutions, Somerset, NJ 08873 USA

Vehicle: The PBO suspension consists of titanium dioxide, microcrystalline cellulose, sodium lauryl sulfate, simethicone, methylparaben, propylparaben, sodium benzoate, citric acid, sodium citrate and is sweetened with sucralose and flavored with artificial cherry.

6.1.3. Blinding the Treatment Assignment

The contents of each bottle will be blinded using labels with unique bottle numbers. Only the IP supplier and the sponsor's IP manager will be unblinded as to the bottle number and the contents of each bottle of IP.

6.2. Administration of Investigational Products

6.2.1. Interactive Web Response System for Investigational Product Management

For the DB phase and the titration period of the OL phase and thereafter an IWRS will be utilized for the following IP tasks:

- Randomization
- Supply management
- Inventory management and supply ordering
- Expiration date tracking
- Emergency unblinding

6.2.2. Allocation of Subjects to Treatment

Subjects will be stratified into 2 groups during the Screening period as either Allo-S biomarker-positive or Allo-S biomarker-negative. A subject will be considered biomarker-positive if her baseline Allo-S level is less than or equal to 2500 pg/mL. Eligible subjects will then be randomly assigned at a 1:1 ratio (GNX:PBO) based on a randomization schedule at Visit 2 (Week 0). Only the IP supplier and the sponsor's IP manager will be unblinded as to the contents of each bottle of IP. Study staff as well as subject and caregiver will be blinded to treatment assignments. In addition, the biomarker group assignment will remain blinded until database unblinding after the study has completed.

An IWRS will centrally randomize subjects. The randomization schedule will be generated using a standard, validated method and maintained by the IWRS vendor and an unblinded statistician. The PI will be instructed by the IWRS, which numbered bottle to use to dose a subject. The PI and research staff will be aware of the ascending dose design of the clinical investigation; however, the PI, the research staff, and the subjects will be blinded with respect to who is receiving active drug versus PBO.

The contents of each bottle will be blinded using labels. The IWRS will use the randomization schedule to match a subject number to a bottle number. Upon completion of baseline evaluations for each subject, the PI or appropriate designee will log into the IWRS to receive assigned bottle(s). Complete instructions for obtaining a bottle number will be provided to the clinical sites prior to initiating the study. The designated personnel at the clinical site will match the assigned bottle number with the correct bottle of IP and distribute the bottle to the PI or designee.

6.2.3. Dosing

6.2.3.1. Double-Blind Period

Ganaxolone is to be administered in increments of 15 mg/kg/day up to 63 mg/kg/day (maximum 1800 mg/day) given as an oral suspension with food. Any subject not tolerating the next dose level can be maintained at the lower dose for additional days before advancing to next dose. If the next dose level is still not tolerated, the subject can drop back to the last tolerated dose. A minimum dose of 33 mg/kg/day or 900 mg/day is generally required following the DB escalation

period, unless a lower dose is agreed to with the Sponsor due to tolerability issues such as somnolence. Dose changes, including alternative dosing paradigm (e.g., lower dose during the daytime and higher dose in the evening) should be discussed with the CRO/sponsor medical monitor prior to making the change or within 48 hours of making the change. Of note, the sponsor defers the final decision to adjust IP to the treating study clinician; dose changes may not exceed the maximum total daily dose defined by the protocol. At each visit, dosing will be reviewed and adjusted as needed based on subject's current weight. Dosing for subjects weighing ≤ 28 kg and > 28 kg is described in Table 3.

Table 3: Oral Suspension (50 mg/ml) Dosing for Subjects Weighing ≤ 28 kg and > 28 kg

Dosing^a for Subjects Weighing ≤ 28 kg (62 pounds)^b			
Dose	Total mg/kg/day	Days	
6 mg/kg TID	18	1-7	
11 mg/kg TID	33	8-14	
16 mg/kg TID	48	15-21	
21 mg/kg TID	63	22-28	

Dosing^a for Subjects Weighing > 28 kg (62 pounds)^c			
Dose	mL per Dose	Total mg/day	Days
150 mg TID	3	450	1-7
300 mg TID	6	900	8-14
450 mg TID	9	1350	15-21
600 mg TID	12	1800	22-28

TID = 3 times daily.

^a To be administered in 3 divided doses following a meal or snack.

^b Subjects weighing ≤ 28 kg (62 pounds) will be dosed according to the subject's weight in kilograms.

^c Subjects > 28 kg will be dosed on a fixed regimen in increments of 150 mg/day up to 1800 mg/day.

Investigational product may be stopped immediately and without down-titration in the case of an emergency, although a down titration in the event of an early termination is recommended. Dose de-escalation (taper) will occur in decreasing increments of 15 mg/kg/day or 450 mg/day approximately every 3 days over 2 weeks whenever feasible (See Section 6.2.3.3 for more details). Taper is not required if the subject is receiving the dose of 18 mg/kg/day or 450 mg/day (or lower).

6.2.3.2. Open-Label Period

Following the completion of the 17-week, DB phase, subjects randomized to PBO will transition to GNX, whereas subjects randomized to GNX will stay on their MTD (minimum of 33 mg/kg/day [900 mg/day]; maximum of 63 mg/kg/day [1800 mg/day]) in a blinded fashion.

Subjects will begin the 4-week blinded dose titration up to 63 mg/kg/day or 1800 mg/day (or MTD) after completing Visit 5. To maintain the blind of the DB phase, subjects initially randomized to GNX will undergo a blinded titration (increasing PBO doses) for 4 weeks, while

PBO subjects will titrate up to 63 mg/kg/day GNX (1800 mg/day maximum or MTD) during the same time period.

Dosing transition from DB to OL for subjects weighing \leq 28 kg and $>$ 28 kg is described in Table 4. All subjects will be dispensed 2 groups of bottles: Bottle Group A (Maintenance) and Bottle Group B (Titration). In addition to the maintenance dose from Bottle Group A, subjects will be instructed to take a second dose from Bottle Group B:

- Subjects initially randomized to GNX: Bottle Group A will contain GNX; Bottle Group B will contain PBO.
- Subjects initially randomized to PBO: Bottle Group A will contain PBO; Bottle Group B will contain GNX.

Dosing from both Bottle Group A and Bottle Group B will begin at the end of Visit 5 (Week 17), the last visit in the DB phase, and continue until the end of the OL 4-week titration period, when subjects return to the site for evaluation (Visit 7, Week 21). Subjects will have an interim safety visit at Visit 6 (Week 19), 2 weeks after starting the OL phase, in which they will receive a new set of medication bottles.

Table 4: Transition from Double-Blind to Open-Label: Dosing for Subjects \leq 28 kg and Subjects $>$ 28 kg

Dosing for Subjects \leq 28 kg (62 pounds)		
Titration Day	Bottle Group A Dose^a	Bottle Group B Dose^b
1-7	63 mg/kg/day (21 mg/kg TID)	18 mg/kg/day (6 mg/kg TID)
8-14	63 mg/kg/day (21 mg/kg TID)	33 mg/kg/day (11 mg/kg TID)
15-21	63 mg/kg/day (21 mg/kg TID)	48 mg/kg/day (16 mg/kg TID)
22-28	63 mg/kg/day (21 mg/kg TID)	63 mg/kg/day (21 mg/kg TID)
Visit 6, Week 21	One set of GNX bottles dispensed, return to dosing from a single bottle (not 2 different ones): 63 mg/kg/day (21 mg/kg TID)	
Dosing for Subjects $>$ 28 kg (62 pounds)		
Titration Day	Bottle Group A Dose^a	Bottle Group B Dose^b
1-7	1800 mg/day; 12 mL per dose TID	450 mg/day; 3 mL per dose TID
8-14	1800 mg/day; 12 mL per dose TID	900 mg/day; 6 mL per dose TID
15-21	1800 mg/day; 12 mL per dose TID	1350 mg/day; 9 mL per dose TID
22-28	1800 mg/day; 12 mL per dose TID	1800 mg/day; 12 mL per dose TID
Visit 6, Week 21	One set of GNX bottles dispensed, return to dosing from a single bottle at a time (not 2 different ones): 1800 mg/day; 12 mL per dose TID	

DB = double-blind, GNX = ganaxolone, TID = 3 times daily.

^a For subjects initially randomized to GNX, Bottle Group A will contain GNX; for subjects initially randomized to placebo, Bottle Group A will contain placebo.

^b For subjects initially randomized to GNX, Bottle Group B will contain placebo; for subjects initially randomized to placebo, Bottle Group B will contain GNX.

Examples of dosing for subjects of different weights are provided in Section 12.3. Dosing instructions for the DB dose titration, DB and OL maintenance and taper are provided in the Pharmacy Manual. Dosing instructions for DB to OL transition are provided in the Pharmacy Manual.

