During the OL phase, all subjects will be treated with GNX. Those subjects who received GNX oral suspension in the 17-week DB phase will receive the same GNX dose in the OL phase of the study. However, to maintain the study blind, GNX subjects will enter into a 4-week blinded titration phase by increasing PBO doses in addition to maintaining GNX. Subjects who received PBO oral suspension in the 17-week DB phase will enter a 4-week, GNX titration period in the OL phase of the study.

Reference Therapy, Dose and Mode of Administration: Placebo is to be administered as an oral suspension TID with food during the 4-week, titration period of the DB phase of the study.

Placebo will only be used in the OL phase of the study during the 4-week blinded titration phase for those subjects who were originally randomized to GNX in the 17-week DB phase.

Duration of treatment: Eligible subjects will collect 12 weeks of prospective baseline seizure data. Subjects will be randomized (1:1 within each biomarker stratum) to a 17-week DB phase with GNX or PBO (4 weeks titration and 13 weeks dose maintenance), followed by a long-term OL treatment phase with GNX. Following the completion of the 17-week DB phase, subjects randomized to PBO will transition to GNX (using blinded titration), while subjects randomized to GNX will stay on 63 mg/kg/day suspension (1800 mg/day maximum), or their maximum tolerated dose (MTD) and also receive a blinded titration of PBO. Subjects will begin the 4-week blinded dose titration to 63 mg/kg/day (1800 mg/day or MTD) after completing the final DB visit. The OL phase will continue until the sponsor terminates the development of the investigational product in PCDH19-related epilepsy or GNX has been approved and marketed in the subjects' respective country.

Participants who complete the study or discontinue investigational product treatment before the end of the study will undergo a 2-week taper period, unless otherwise medically indicated, after which she will return to the study site for a safety follow up visit. Subjects who discontinue investigational product treatment before the completion of the DB phase will continue to be followed per protocol and, at a minimum, subjects will be encouraged to maintain daily seizure eDiary entries until the DB phase is completed.

Criteria for Evaluation:

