12.3. Appendix 3: Examples of Dosing Titration for Oral Suspension

An example of the transition from DB to OL dosing is shown below for a 20-kg subject who was initially randomized to GNX during the DB phase:

Titration Day	Bottle Group A- Maintenance Treatment: GNX	Bottle Group B- Titration Treatment: Placebo
Days 1-7	63 mg/kg/day (21 mg/kg TID)	18 mg/kg/day (6 mg/kg TID)
Morning dose	21 mg/kg; 8.4 mL	6 mg/kg; 2.4 mL
Afternoon dose	21 mg/kg; 8.4 mL	6 mg/kg; 2.4 mL
Evening dose	21 mg/kg; 8.4 mL	6 mg/kg; 2.4 mL
Continue dosing from Group A and B as above until the end of Day 7		
Days 8-14	63 mg/kg/day (21 mg/kg TID)	33 mg/kg/day (13 mg/kg TID)
Morning dose	21 mg/kg; 8.4 mL	11 mg/kg; 4.4 mL
Afternoon dose	21 mg/kg; 8.4 mL	11 mg/kg; 4.4 mL
Evening dose	21 mg/kg; 8.4 mL	11 mg/kg; 4.4 mL
Continue dosing from Group A and B as above until end of Day 14		
Days 15-21	63 mg/kg/day (21 mg/kg TID)	48 mg/kg/day (16 mg/kg TID)
Morning dose	21 mg/kg; 8.4 mL	16 mg/kg; 6.4 mL
Afternoon dose	21 mg/kg; 8.4 mL	16 mg/kg; 6.4 mL
Evening dose	21 mg/kg; 8.4 mL	16 mg/kg; 6.4 mL
Continue dosing from Group A and B as above until the end of Day 21		
Days 22-28	63 mg/kg/day (21 mg/kg TID)	63 mg/kg/day (21 mg/kg TID)
Morning dose	21 mg/kg; 8.4 mL	21 mg/kg; 8.4 mL
Afternoon dose	21 mg/kg; 8.4 mL	21 mg/kg; 8.4 mL
Evening dose	21 mg/kg; 8.4 mL	21 mg/kg; 8.4 mL
Continue dosing from Group A and B as above until Visit 6, Week 21		
Visit 6, Week 21	One set of GNX bottles dispensed, return to dosing from 1 bottle at a time	
Day 29	63 mg/kg/day (21 mg/kg TID)	
Morning dose	21 mg/kg; 8.4 mL	
Afternoon dose	21 mg/kg; 8.4 mL	
Evening dose	21 mg/kg; 8.4 mL	

GNX = ganaxolone, TID = 3 times daily.

An example of the transition from DB to OL dosing is shown below for a 20-kg subject who was initially randomized to PBO during the DB phase:

Titration Day	Bottle Group A- Maintenance Treatment: Placebo	Bottle Group B- Titration Treatment: GNX
Days 1-7	63 mg/kg/day (21 mg/kg TID)	18 mg/kg/day (6 mg/kg TID)
Day 1 morning dose	21 mg/kg; 8.4 mL	6 mg/kg; 2.4 mL
Day 1 afternoon dose	21 mg/kg; 8.4 mL	6 mg/kg; 2.4 mL
Day 1 evening dose	21 mg/kg; 8.4 mL	6 mg/kg; 2.4 mL
Continue dosing from Group A and B as above until the end of Day 7		
Days 8-14	63 mg/kg/day (21 mg/kg TID)	33 mg/kg/day (11 mg/kg TID)
Day 8 morning dose	21 mg/kg; 8.4 mL	11 mg/kg; 4.4 mL
Day 8 afternoon dose	21 mg/kg; 8.4 mL	11 mg/kg; 4.4 mL
Day 8 evening dose	21 mg/kg; 8.4 mL	11 mg/kg; 4.4 mL

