Continue dosing from Group A and B as above until end of Day 14		
Days 15-21	63 mg/kg/day (21 mg/kg TID)	48 mg/kg/day (16 mg/kg TID)
Day 15 morning dose	21 mg/kg; 8.4 mL	16 mg/kg; 6.4 mL
Day 15 afternoon dose	21 mg/kg; 8.4 mL	16 mg/kg; 6.4 mL
Day 15 evening dose	21 mg/kg; 8.4 mL	16 mg/kg; 6.4 mL
Continue dosing from Group A and B as above until the end of Day 21		
Days 22-28	63 mg/kg/day (21 mg/kg TID)	63 mg/kg/day (21 mg/kg TID)
Day 15 morning dose	21 mg/kg; 8.4 mL	21 mg/kg; 8.4 mL
Day 15 afternoon dose	21 mg/kg; 8.4 mL	21 mg/kg; 8.4 mL
Day 15 evening dose	21 mg/kg; 8.4 mL	21 mg/kg; 8.4 mL
Continue dosing from Group A and B as above until Visit 6, Week 21		
Visit 6, Week 21	One set of GNX bottles dispensed, return to dosing from 1 bottle at a time	
Day 29	63 mg/kg/day (21 mg/kg TID)	
Day 29 morning dose	21 mg/kg; 8.4 mL	
Day 29 afternoon dose	21 mg/kg; 8.4 mL	
Day 29 evening dose	21 mg/kg; 8.4 mL	

GNX = ganaxolone, TID = 3 times daily.

An example of the transition from DB to OL dosing is shown below for a > 28-kg subject who was initially randomized to GNX during the DB phase:

Titration Day	Bottle Group A- Maintenance Treatment: GNX	Bottle Group B- Titration Treatment: Placebo
Days 1-7	1800 mg/day (600 mg TID)	450 mg/day (150 mg TID)
Day 1 morning dose	600 mg; 12 mL	150 mg; 3 mL
Day 1 afternoon dose	600 mg; 12 mL	150 mg; 3 mL
Day 1 evening dose	600 mg; 12 mL	150 mg; 3 mL
Continue dosing from Group A and B as above until the end of Day 7		
Days 8-14	1800 mg/day (600 mg TID)	900 mg/day (300 mg TID)
Day 8 morning dose	600 mg; 12 mL	300 mg; 6 mL
Day 8 afternoon dose	600 mg; 12 mL	300 mg; 6 mL
Day 8 evening dose	600 mg; 12 mL	300 mg; 6 mL
Continue dosing from Group A and B as above until end of Day 14		
Days 15-21	1800 mg/day (600 mg TID)	1350 mg/day (450 mg TID)
Day 15 morning dose	600 mg; 12 mL	450 mg; 9 mL
Day 15 afternoon dose	600 mg; 12 mL	450 mg; 9 mL
Day 15 evening dose	600 mg; 12 mL	450 mg; 9 mL
Continue dosing from Group A and B as above until the end of Day 21		
Days 22-28	1800 mg/day (600 mg TID)	1800 mg/day (600 mg TID)
Day 15 morning dose	600 mg; 12 mL	600 mg; 12 mL
Day 15 afternoon dose	600 mg; 12 mL	600 mg; 12 mL
Day 15 evening dose	600 mg; 12 mL	600 mg; 12 mL
Continue dosing from Group A and B as above until Visit 6, Week 21		
Visit 6, Week 21	One set of GNX bottles dispensed, return to dosing from 1 bottle at a time	
Day 29	1800 mg/day (600 mg TID)	
Day 29 morning dose	600 mg; 12 mL	
Day 29 afternoon dose	600 mg; 12 mL	

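### Table 4 prints only the full ganaxolone dose for Bottle A and for Week 21, although Section 6.2.3.2 of the protocol allows the maximum tolerated dose

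*Protocol*

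**What the plan says.** The protocol text allows reduced doses in the open-label phase. Section 6.2.3.2 states that "subjects randomized to GNX will stay on their MTD (minimum of 33 mg/kg/day [900 mg/day]; maximum of 63 mg/kg/day [1800 mg/day", and for the other arm that "PBO subjects will titrate up to 63 mg/kg/day GNX (1800 mg/day maximum or MTD) during the same time period". The synopsis agrees: subjects who were on ganaxolone (GNX) "will receive the same GNX dose in the OL phase of the study". Section 3.2 also names the MTD.

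During the four-week blinded titration every subject takes two sets of bottles. Bottle Group A holds GNX for subjects from the GNX arm and placebo (PBO) for subjects from the PBO arm; Bottle Group B is the reverse. Section 6.2.2 keeps the investigator, staff, subject and caregiver blinded.

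Table 4 prints Bottle A at 63 mg/kg/day, or 1800 mg/day above 28 kg, in every titration week. At Visit 6 (Week 21) all subjects change to a single set of GNX bottles. The row for children up to 28 kg reads "One set of GNX bottles dispensed, return to dosing from a single bottle (not 2 different ones): 63 mg/kg/day (21 mg/kg TID". The row for heavier children says to "return to dosing from a single bottle at a time (not 2 different ones): 1800 mg/day; 12 mL per dose TID". Neither has an MTD alternative or footnote. The four tables in Section 12.3 show the same full doses for Bottle A and Day 29.

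Section 6.2.3.2 also says where the operating detail sits: "Dosing instructions for DB to OL transition are provided in the Pharmacy Manual". That manual is not among the documents reviewed.

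**The concern.** Subjects on less than the full dose are foreseen. Sections 3.1, 3.4 and 6.2.3.1 let a child who cannot tolerate the top dose stay on a lower one, generally not below 33 mg/kg/day or 900 mg/day. For such a child from the GNX arm, the only Week 21 dose printed in Table 4 is not the dose that the text above it prescribes.

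Blinding makes this harder for a site to notice. Take a child who ends the titration with A held at 33 mg/kg/day and B raised to 63. If she came from GNX, her active dose is the A dose, 33. If she came from PBO, she has been taking 63 of active drug from B. The site cannot tell which applies, and the printed row gives 63 for both. A site could follow that row in good faith and nearly double the active dose of a child whose dose had been held down for tolerability. What is at stake is dosing safety in the open-label phase.

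**Working it through.** **Inputs.** Dose ladder: 18, 33, 48, 63 mg/kg/day, or 450, 900, 1350, 1800 mg/day, seven days per level (Table 3). Suspension strength: 50 mg/mL (Section 6). Range for continuing GNX subjects: 33 to 63 mg/kg/day or 900 to 1800 mg/day (Section 6.2.3.2). Week 21 entries: 63 mg/kg/day or 1800 mg/day (Table 4).

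**Reproducing the printed volumes.** Volume per dose = mg/kg per dose x weight / 50. The worked example "for a 20-kg subject who was initially randomized to GNX during the DB phase" gives 21 x 20 / 50 = 8.4 mL for the full dose and 11 x 20 / 50 = 4.4 mL for the 33 mg/kg/day level. Above 28 kg, 600 / 50 = 12 mL. All match Section 12.3, so the printed full-dose figures are arithmetically right. The issue is whom they fit.

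**Change if A is kept at the MTD and the Week 21 row is then followed.** Ratio = printed dose / MTD; steps = difference / 15 mg/kg/day or / 450 mg/day.

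| MTD | Printed Week 21 dose | Ratio | Ladder steps |
|---|---|---|---|
| 33 mg/kg/day | 63 | 63/33 = 1.91 | (63 - 33)/15 = 2 |
| 48 mg/kg/day | 63 | 63/48 = 1.31 | (63 - 48)/15 = 1 |
| 900 mg/day | 1800 | 1800/900 = 2.0 | (1800 - 900)/450 = 2 |
| 1350 mg/day | 1800 | 1800/1350 = 1.33 | (1800 - 1350)/450 = 1 |

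At 20 kg, 33 to 63 mg/kg/day is 33 x 20 = 660 to 63 x 20 = 1260 mg/day, or 4.4 to 8.4 mL three times daily. The two-step cases skip a level that Table 3 would hold for seven days. The one-step cases skip nothing on the ladder, but they still take the child above her MTD.

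**Timing.** Enrollment stopped on 01 July 2020 (Synopsis), and this amendment is dated 20 January 2021. Week 21 is 147 days after randomization. Table 1, footnote r, allows 84 to 90 days from screening to randomization, and Visit 6 has a window of 3 days either way.

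- If the last subject was screened on 01 July 2020: + 84 + 147 days = 17 February 2021, and + 90 + 147 + 3 days = 26 February 2021.
- If randomization itself stopped on that date: + 147 days = 25 November 2020.

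The last planned Week 21 visit is therefore either before the amendment or 28 to 37 days after it.

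**The case against.** The strongest reply is that the text governs. Section 6.2.3.2 states the MTD just before the table, and the synopsis and Section 3.2 agree. Table 3 likewise prints only the full ladder and leaves flexibility to the text. Section 12.3 is headed as examples, so full-dose cases there are not a contradiction. Section 3.4 lets a subject fall back to a tolerated dose, sends dose changes to the medical monitor and leaves the final decision to the treating clinician. There are calls three days after Visit 5 and at Weeks 18, 19 and 20, and Visit 6 is a clinic visit.

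Much of this stands. It answers the objection to Section 12.3, and it means that intolerance would probably be noticed. It does not put the MTD into Table 4, and none of these provisions tells a blinded clinician which bottle held active drug.

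A second reply is that the jump at Week 21 needs a mixed reading: the text for Bottle A over four weeks, then the table for the next row. A site that took the whole table literally would already have raised A at the start of the titration. That is true, and the ratios above are conditional on the mixed reading. But the literal reading departs from the MTD text as well, by the same ratio and sooner.

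A reader might go further and infer that no rule exists for unequal A and B doses. The documents do not show that. The protocol assigns transition dosing to the Pharmacy Manual, which may hold the rule. The SAP's silence proves nothing, since its introduction refers readers to the protocol for study conduct.

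**Conclusion.** The mismatch is real and minor. Table 4 lacks the MTD option that its own section prescribes, and its Week 21 entry is wrong for a GNX-arm child on a reduced dose. If A is kept at the MTD and that row is followed, active drug rises by x1.31 to x2.0 in one move. The documents do not give the number of reduced-dose subjects, so no frequency is claimed. Many transitions may be past, under the timing assumptions shown. The 17-week primary analysis is not affected.

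Three stronger readings are tempting and not supported:

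- **Larger jumps from a sponsor-agreed dose below the minimum.** The protocol allows such agreements but names no such dose, so there is no documented starting point.
- **A distorted open-label exposure summary.** SAP Section 9 reports the highest percentage of the maximum daily dose that was received. If a child did receive the top dose, reporting 100% is correct.
- **A need for someone unblinded to set the Week 21 dose.** Where A and B differ, the issued dose could reveal the arm. That trade-off is not justified while the Pharmacy Manual may already deal with the case.

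**What to change.** 1. In both weight bands of Table 4, change the Bottle Group A entries to: *the subject's DB maintenance dose (MTD), up to 63 mg/kg/day or 1800 mg/day*.
2. Change the Visit 6, Week 21 entries to: *the tolerated GNX dose (MTD), up to 63 mg/kg/day or 1800 mg/day*.
3. Add a note to Section 12.3 that the examples show the full-dose case.
4. Check that the Pharmacy Manual's transition instructions cover subjects whose A and B doses differ, then cross-reference them for those subjects in Section 6.2.3.2.

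The Bottle Group B ladder can stay as printed. The cost is a few table entries, one note, one cross-reference and one check of an existing manual, with no added visits, subjects or analyses.
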